Primary outcomes:

- DNA fragmentation as a predictor of clinical pregnancy and live birth rate

Secondary outcomes:

- DNA fragmentation in the total and vital fraction before and after density gradient in the diagnostic sample (pre-IUI)
- DNA fragmentation in the total and vital fraction before and after density gradient in the therapeutic sample (IUI sample)
- DNA fragmentation in relation to the cumulative clinical pregnancy and live birth rate

Study Phase & Design

Prospective interventional study
Duration: 24 months

Source population: couples with unexplained, mild male infertility, mild endometriosis defined by revised American Society for Reproductive Medicine stage I and II

Single center, university setting, no commercial affiliation

Study Population

Inclusion criteria:

Couples seeking fertility treatment after at least 12 months of unprotected intercourse are eligible. All couples underwent basic fertility investigations which included semen analysis, evaluation of menstrual cycle, and tubal patency testing (Chlamydia antibody test, hysterosalpingography/HyfoSy or laparoscopy).

All participating couples should provide written informed consent

Inclusion criteria are

- Unexplained infertility
 - o We classify couples as having unexplained subfertility when the fertility investigations showed at least one patent fallopian tube, a normal ovulatory

- menstrual cycle (26-32), and a normal semen analysis (pre-wash total motile sperm count above 10 million).
- Mild male infertility defined as one or more abnormal semen parameters according to the WHO 2010 criteria on at least two examinations; diagnosis is determined by most abnormal result
- Women: age between 18 and 40 years, BMI between 18,5-30, presence of at least one patent tube on hysterosalpingography/Hysterosalpingo foam sonography (Hyfosalpingo) and/or laparoscopy, normal uterine cavity (ultrasound, hysterosalpingography or laparoscopy), regular menstrual cycle (24-38 days, FIGO recommendations 2011)
- Men: age between 18 and 65 years, BMI between 18,5-30, normal semen analysis or mild male subfertility
- Exclusion criteria: double sided tubal disease, severe endometriosis (classified as revised American Society for Reproductive Medicine stage III or IV), premature ovarian failure, and known endocrine disorders (such as Cushing's syndrome or adrenal hyperplasia), azoö- or necrozoöspermia

Statistics

- Sample size: 120 patients

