A power analysis was performed to estimate the sample size needed for ROC curve analysis. Since there is scarce literature for sperm DNA fragmentation on an IUI sample both before and after gradient, we cannot rely on reference values to estimate the area under the curve (AUC) or distribution of cases versus controls (kappa). In function of a significance of 0,05 (type I error) and power of 0,8 (1-type II error), a kappa varying between 1:1 and 1:3 and AUC varying between 0,7-0,75 we estimate a minimum of 38 patients and a maximum of 130 patients should be included.
- Diagnostic parameters: sensitivity, specificity, area under receiver operator curve, predictive value, likelihood ratio, odds ratio
- Null hypothesis:
 - 1) There is no correlation between DNA fragmentation and clinical pregnancy/live birth after IUI
 - 2) Density gradient isn't capable of selecting motile sperm with low DNA fragmentation for insemination

Clinical protocol

- IUI in a spontaneous cycle
- Basal ultrasound and hormonal analysis on cycle day 2 or 3 (estradiol (E2), progesterone (P), luteinizing hormone (LH) as well as follicle stimulating hormone (FSH))
- Cycle monitoring from D10-12 with ultrasound and/or hormonal analysis (E2, P, LH)
- 250 microgram hCG or 5000 IU is administered to induce ovulation when a maximum of 2 dominant follicles are present. Either Pregnyl, Choragon, Ovitrelle will be used
- IUI is planned between 32-40 hours after HCG administration or \pm 24-26 hours after detection of spontaneous LH surge
- Both ultrasound and hormonal analysis (E2, P, LH) are done on the day of planning of IUI (day of hCG administration or day of LH surge)
- Sperm preparation is performed according to local validated procedures in accordance with the 2010 WHO criteria. DNA fragmentation analysis by TUNEL assay will be carried out both before and after density gradient.
- Patients are advised to rest in the supine position during 15 minutes immediately after IUI according to evidence from a RCT (Custers et al. 2009)
- Detection of pregnancy
 - β HCG testing is performed 15-20 days after insemination
 - A second β HCG testing is performed 7 days later to confirm a positive evolution of pregnancy
 - In case of a positive evolution of β HCG an ultrasound is performed around 5-6 weeks after IUI
 - Follow-up of pregnancy until birth through staff, telephone or e-mail contact until birth

- Items to be registered

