 - Number of eligible patients (patients who fulfilled inclusion criteria and to whom the study was proposed)
 - Number of drop outs between inclusion and end of treatment
 - Number of spontaneous pregnancies between inclusion and end of treatment
 - Number of live births between inclusion and end of treatment

 - Hunault score and modified Hunault-score according to Bendsorp et al.
 - All Belrap items
 - Semen analysis methodology checklist according to Björndahl et al. (Appendix)
 - Patient population characteristics:
 - Infertility: duration, primary versus secondary, female/male/mixed/unexplained
 - Cause of female infertility: Ovulatory disorder, Anatomical infertility, Endometriosis (revised American Society for Reproductive Medicine classification) or Adenomyosis
 - Possible cause of male infertility: Varicocele, Cryptorchidism, Male accessory gland infections, Germ cell malignancies and testicular microcalcifications, Disorders of ejaculation, Idiopathic. Primary spermatid failure, genetic disorders of infertility, obstructive azoospermia, hypogonadism were not reported since azoospermia is considered an exclusion criterium.

- Data analysis and Publication policy
Data analysis and preparation for publication will be done at the University Hospital of Antwerp / University of Antwerp.

References

de Kretser DM. Male infertility. *Lancet.* 1997; 15: 349(9054):787-790.

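### Is a target of 120 patients too small when the plan's own power calculation runs up to 130?

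*Combined protocol and SAP*

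**What the plan says.** The Statistics section opens with the target, "Sample size: 120 patients". The power analysis for the ROC curve follows. It explains that literature on the IUI sample before and after gradient is scarce, so that "we cannot rely on reference values to estimate the area under the curve (AUC) or distribution of cases versus controls (kappa"). It then takes a significance level of 0.05 and power of 0.8, with "a kappa varying between 1:1 and 1:3 and AUC varying between 0,7-0,75", and reports the result as a range: "we estimate a minimum of 38 patients and a maximum of 130 patients should be included".

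The plan does not give the formula, the sidedness of the test or the null AUC. It does not say why 120 was chosen, or whether the numbers mean couples enrolled or couples with a known outcome. Under the items to be registered, the Clinical protocol lists "Number of drop outs between inclusion and end of treatment" and "Number of spontaneous pregnancies between inclusion and end of treatment", but no loss rate or inflation of the sample size appears anywhere.

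**The concern.** A plan that cannot rank its scenarios would normally be sized for the worst of them. Here the worst scenario asks for 130 and the target is 120, with no reason given. The plan also expects drop-outs and spontaneous pregnancies, so fewer than 120 couples may contribute to the ROC analysis.

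If 130 is truly what 80% power requires at AUC 0.70 and one case per three controls, the study would fall below its stated power there, and further below with each loss. A negative ROC result could then be dismissed because the study was smaller than its own calculation asked for.

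**Working it through.** **Inputs.** From the Statistics section: target 120, range 38 to 130, alpha 0.05, power 0.80, AUC 0.70 to 0.75, ratio 1:1 to 1:3. Assumed, because the plan is silent: null AUC 0.5, the variance formula, the sidedness, and loss rates of 10% and 20%.

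**Step 1: reproduce 38 and 130.** One rule returns both ends at the expected corners. It uses the upper bound Var(AUC) ≤ A(1 − A)/min(cases, controls), with one-sided alpha (z = 1.645) and z = 0.842 for power:

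n(smaller group) = (1.645 + 0.842)² × A(1 − A)/(A − 0.5)²

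- A = 0.75: 6.183 × 0.1875/0.0625 = 18.55. At 1:1 the total is 37.1, rounded up to 38.
- A = 0.70: 6.183 × 0.21/0.04 = 32.46. At 1:3 the total is 129.8, rounded up to 130.

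The full grid on this rule is:

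| AUC | 1:1 | 1:2 | 1:3 |
|---|---|---|---|
| 0.75 | 38 | 56 | 75 |
| 0.70 | 65 | 98 | 130 |

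So 120 covers five of these six scenarios and misses one. The match does not prove that the sponsor used this bound.

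**Step 2: power of 120 in the missed corner (AUC 0.70, 1:3).** With 30 cases, the bound gives Φ(0.20/√(0.21/30) − 1.645) = Φ(0.745) = 0.77. With 108 analysed (10% loss) it gives 0.73, and with 96 (20% loss) 0.69. Taking 130 simply as the N for 80% power in a two-sided test gives nearly the same: Φ(2.802 × √(120/130) − 1.960) = Φ(0.732) = 0.77.

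**Step 3: the same corner with a standard variance.** The two-sided Obuchowski binormal formula, with k controls per case, is:

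- a = 1.414 × z(AUC) = 1.414 × 0.5244 = 0.7415
- V₀ = 0.0792(1 + 1/k) = 0.1056 at k = 3
- V = 0.0099 e^(−a²/2)[(5a² + 8) + (a² + 8)/k] = 0.1023
- cases = [1.960√0.1056 + 0.842√0.1023]²/0.20² = 20.5

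The total is 20.5 × 4 = 82.1, or 84 when rounded to whole groups (21 + 63). The Hanley–McNeil variance gives 88. The Obuchowski formula also returns 38 for AUC 0.75 at 1:1, but it does not return 130.

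Power at AUC 0.70 and 1:3 is then Φ[(0.20√cases − 1.960√0.1056)/√0.1023]:

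| Analysed | Cases | Power, bound (one-sided) | Power, Obuchowski (two-sided) |
|---|---|---|---|
| 120 | 30 | 0.77 | 0.92 |
| 108 | 27 | 0.73 | 0.90 |
| 96 | 24 | 0.69 | 0.86 |

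A simulation with normal scores of equal variance and a two-sided rank-sum test at 0.05 (4,000 runs per sample size) agreed with the last column to within one percentage point.

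**Step 4: tolerance to losses.** If the worst corner needs 84, then 120 tolerates 1 − 84/120 = 30% loss. If it needs 88, it tolerates 1 − 88/120 = 27%.

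**The case for a change.** The strongest case for a change is that the sponsor's own figure is 130, and a reviewer's formula should not be used to explain it away. On that figure 120 is short, whatever method produced it. The shortfall of about 3 points before losses does not depend on the bound. The unbalanced end of the range cannot be called remote either. The Introduction does say that about 50% of patients are not pregnant after 4–6 cycles, which points to roughly 1:1. But that is a cumulative figure, and the cumulative outcome is listed as secondary. The per-cycle rates of 5–13% quoted there are more unbalanced than 1:3. A sentence or two of explanation would be cheap.

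Part of this stands. The choice of 120 is unexplained, and naming the method would have helped the reader. The rest does not support a change:

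- A span from minimum to maximum across assumptions is a sensitivity range. It does not commit the study to the maximum, and a target near its top is a fair compromise for a single-centre study planned to last 24 months.
- If the bound lies behind 130, the 0.77 is a floor and not the expected power.
- If the analysis were per first cycle at 5–13%, the whole ratio range would be in question. That is a separate matter of the unit of analysis, and moving from 120 to 130 would not settle it.
- Stopping treatment is not the same as being lost to the ROC analysis. A couple that stops after an insemination may still have a sample and an outcome, and the Clinical protocol plans follow-up of pregnancies until birth.

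**Conclusion.** The concern is accurate on the text but calls for no change. The plan makes an unexplained choice inside its own range. It does not contradict itself, and no loss of power is demonstrated.

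Taking 130 at face value, the gap is 10 of 130 patients, about 3 points of power, in one corner (AUC 0.70, 1:3). On the standard two-sided formula, 120 exceeds every requirement on the stated grid and leaves room for roughly 27–30% loss. These results assume a null AUC of 0.5 and, for the 0.92 and 0.86, binormal scores. The loss rates are illustrative because the documents give none.

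Enrolling 130 with known outcomes would take 130/0.9 = 145 couples at 10% loss or 130/0.8 = 163 at 20%. That is 25 to 43 more than planned, to close a gap that may exist only on paper. Writing down the reason for 120 would be good reporting, but it would alter neither the couples studied nor the analysis. At the end of the study, the numbers of cases and controls actually analysed and the confidence interval for the AUC will show how informative a negative result is, more directly than any comparison of 120 with 130.

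### Does the missing rule for couples who conceive spontaneously, or whose birth outcome stays unknown, undermine the analysis of live birth after IUI?

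*Combined protocol and SAP*

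**What the plan says.** In the combined protocol and SAP, the first null hypothesis under Statistics reads: "There is no correlation between DNA fragmentation and clinical pregnancy/live birth after IUI". Under Study Endpoints, the primary outcome is "DNA fragmentation as a predictor of clinical pregnancy and live birth rate", and one secondary outcome is "DNA fragmentation in relation to the cumulative clinical pregnancy and live birth rate". Neither endpoint names the mode of conception.

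The list headed Items to be registered has two neighbouring lines, "Number of spontaneous pregnancies between inclusion and end of treatment" and "Number of live births between inclusion and end of treatment". Drop-outs are counted there too.

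Under Clinical protocol, Detection of pregnancy, the hCG tests and the ultrasound are timed from the insemination, followed by "Follow-up of pregnancy until birth through staff, telephone or e-mail contact until birth".

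The Statistics section plans a ROC analysis ("Sample size: 120 patients"; "a kappa varying between 1:1 and 1:3 and AUC varying between 0,7-0,75") and lists diagnostic measures. It gives no rule for spontaneous conceptions or for birth outcomes that cannot be obtained.

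**The concern.** A ROC analysis needs every unit to be a case or a control. The plan expects some spontaneous pregnancies, since it counts them, and eligible women have a regular cycle and at least one open tube. Three treatments of these couples can be defended, and each can give a different answer:

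- As IUI failures, they put men whose sperm achieved a pregnancy among the controls.
- As successes, they credit IUI with births it did not produce.
- Left out, they shrink the sample after inclusion.

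The same choice arises for a pregnancy whose outcome staff cannot trace. If the label were chosen after the TUNEL results were known, a primary result could be steered. The live-birth count also stops at the end of treatment, a point the plan does not define, while follow-up runs to birth. Read literally, that count would miss later births.

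**Working it through.** **What the text supports.** The title concerns pregnancy outcome after insemination. Study Objectives asks who benefits from IUI. The null hypothesis says after IUI. Pregnancy detection starts from a dated insemination and runs to birth. Against these stands one registration line that is silent on origin and sits directly below a separate line for spontaneous pregnancies. Nothing in the plan labels a spontaneous birth as an IUI success. Follow-up to birth captures births after treatment ends, so the narrower window in the tally is loose wording and does not lose data.

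**The plan's own figure.** The plan gives 38 to 130 patients for AUC 0.70–0.75 and ratios 1:1 to 1:3. At AUC 0.75 and 1:1, two-sided 0.05 and power 0.80, the Hanley-McNeil variance gives 40 and a binormal variance gives 38, so the minimum is reproduced. The largest Hanley-McNeil figure in the stated ranges is 88 (AUC 0.70, 1:3), so 130 is not reproduced. The present point does not depend on it.

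**Inputs for the size.** From the plan: N = 120, and C = 60 or 30 IUI births (ratio 1:1 or 1:3). Assumed: one label per couple, true AUC A = 0.70, and S = 12 spontaneous conceivers (10%; range 6–18). The remaining controls are R = 120 − C − S.

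**Formulas.** If the S couples are labelled controls but resemble cases, AUC = (R·A + S·0.5)/(R + S). If they are labelled cases but resemble controls, AUC = (C·A + S·0.5)/(C + S). If they lie halfway, 0.5 is replaced by (0.70 + 0.50)/2 = 0.60. With m cases and n controls,

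SE² = [A(1−A) + (m−1)(A/(2−A) − A²) + (n−1)(2A²/(1+A) − A²)]/(mn),

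and power = Φ((AUC − 0.5 − 1.96·SE₀)/SE₁), where SE₀ is taken at AUC 0.5 and SE₁ at the AUC in question.

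**Couples left out.** For 60 v 48, SE₁ = 0.0498 and SE₀ = 0.0562, so power = Φ((0.20 − 0.1101)/0.0498) = 0.965. For 30 v 78, SE₁ = 0.0595 and power is 0.905. The AUC stays at 0.70.

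**Couples labelled, S = 12.** Each cell gives C = 60, then C = 30.

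| What the 12 couples resemble | Labelled controls: AUC; power | Labelled cases: AUC; power |
|---|---|---|
| Cases | 0.660, 0.673; 0.872, 0.815 | 0.700, 0.700; 0.977, 0.960 |
| Halfway | 0.680, 0.687; 0.941, 0.870 | 0.683, 0.671; 0.946, 0.881 |
| Controls | 0.700, 0.700; 0.978, 0.914 | 0.667, 0.643; 0.892, 0.735 |

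Examples: (48 × 0.70 + 12 × 0.5)/60 = 0.660; (30 × 0.70 + 12 × 0.5)/42 = 0.643.

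The first and last rows cannot both be true of the same couples. In each of them, one label costs 0.027 to 0.057 of AUC and the other costs nothing. In the halfway row both labels cost 0.013 to 0.029, and power stays at 0.87 or above. The losses compare with standard errors of 0.050 and 0.060.

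Over 6 to 18 couples, the unfavourable cells span AUC 0.625–0.687 and power 0.64–0.95. At a true AUC of 0.75 with 12 couples, they give AUC 0.68–0.72 and power of at least 0.906.

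**Unknown birth outcome.** Assume 6 of 60 pregnancies are untraced and every traced one ends in a birth. The live birth rate is 54/120 = 45.0% if they count as no birth and 54/114 = 47.4% if left out. The 95% half-width is 1.96 × √(0.45 × 0.55/120) = 0.089, so a gap of 2.4 points is small against about 9. The AUC with the no-birth label is (60 × 0.70 + 6 × 0.5)/66 = 0.682. With 30 births and 6 untraced, the AUC is (90 × 0.70 + 6 × 0.5)/96 = 0.688 and power is 0.814, against 0.859 if they are left out.

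**The case for a change.** The strongest case for a change is that the rule is absent from the whole plan, whatever one makes of the registration list. Being able to identify IUI births does not say where spontaneous conceivers go, and a written rule would cost a paragraph. The silence is conceded, and so is the arithmetic: in the least favourable cells (30 births, spontaneous conceivers counted as cases and resembling controls) power falls to 0.735 with 12 couples and 0.641 with 18.

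Three things limit it.

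- The unit of analysis is not fixed as the couple. The Introduction quotes pregnancy rates per cycle, and TUNEL is run with the sperm preparation for insemination. In a per-cycle analysis, a conception in a cycle without insemination adds no row. A couple who conceives before any IUI has no IUI sample to enter under any label.
- The 60-birth scenario with 12 spontaneous conceivers has (60 + 12)/120 = 60% conceiving, although the Introduction says about half do not become pregnant after 4–6 IUI cycles.
- The specific rules one might write are open to dispute. Leaving couples out because of an event after inclusion is a selection. Censoring at spontaneous conception treats a competing event as uninformative and would overstate a cumulative IUI rate.

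That a label could be chosen after seeing the results is a possibility; nothing in the plan suggests that it would be.

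**Conclusion.** No change to the plan follows. The missing rule is a detail that analysts can fill from the plan's own purpose: cases are clinical pregnancies or live births from an IUI conception, and spontaneous and untraced pregnancies are counted and reported. The plan already counts spontaneous pregnancies and follows pregnancies to birth. Beyond that, whether to leave such couples out, relabel them or treat them as a competing event is a trade-off on which careful statisticians differ. No stated rule has been shown to give a wrong result.

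The documents give no rate of spontaneous conception or of lost birth outcomes, so the size cannot be fixed. On the assumption of 12 couples, one label each, 30 or 60 IUI births and a true AUC of 0.70, the AUC loss is at most 0.03 to 0.06 and power falls below 0.80 in one of the twelve cells. That the gap exists is certain; its practical weight is a judgement resting on these assumptions.

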In this prospective cohort study we aim to investigate the role of sperm DNA fragmentation analysis in selecting the patient who will benefit from intra-uterine insemination (IUI) therapy since IUI is still considered the first step in MAR and is performed at a large scale in Belgium and worldwide.

The overall success rate of IUI remains controversial. On average, reported clinical pregnancy rates are only 5–13% per IUI cycle (Bensdorp et al., 2007; Goverde et al., 2000; Guzick et al., 1999; Nyboe Andersen et al., 2009; Steures et al., 2004, 2007; The ESHRE Capri Workshop Group, 2009; Tummon et al., 1997; Verhulst et al., 2006).

A Cochrane analysis pointed to the position of IUI in male subfertility treatment as being one of the most frequently used treatments (Veltman-Verhulst et al., 2016) although its efficacy in the setting of mild male/unexplained infertility is yet to be proven. The authors concluded that there was insufficient evidence of effectiveness to recommend or advise against IUI.

In addition, the literature pertaining IUI consists of a broad range of indications for therapy, ranging from but not limited to: unexplained fertility, mild male infertility and mild endometriosis. Respectively, each of these diagnoses also have slightly different definitions from one study to another, thus making a univocal recommendation concerning IUI very challenging.

Our goal would be to better select patients for IUI, widely considered less invasive and expensive therapy than others, as about 50% of the patients entering an IUI program will not become pregnant after 4-6 IUI cycles and thus in selected cases (Van Hoof et al., 2009) progression to more advanced fertility therapy could be beneficial.

Study Objectives

The objective is to test the hypothesis that DNA fragmentation testing can play a diagnostic and thus pivotal role in selecting the patient who will benefit from intra-uterine insemination (IUI) therapy leading to a higher clinical pregnancy and live birth rate (primary outcomes) compared to the standard semen criteria.

Additionally, DNA fragmentation will be measured both at the time of the diagnostic work-up as at the time of insemination with evaluation in the neat and washed specimen, both in the total and vital fraction. We aim to assess whether density gradient retrieves high quality motile sperm with little DNA damage and where DNA fragmentation testing best fits in the clinical patient pathway (secondary outcomes).

Study Endpoints

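### The listed measures describe DNA fragmentation on its own, so they cannot show that it adds to standard semen criteria or to the prognostic factors the study registers

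*Combined protocol and SAP*

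**What the plan says.** The objective (Study Objectives) is comparative. Fragmentation testing is to identify the couples who benefit from IUI, with better pregnancy and live birth rates "compared to the standard semen criteria". The primary outcome (Study Endpoints) is "DNA fragmentation as a predictor of clinical pregnancy and live birth rate". Cumulative pregnancy and live birth are secondary.

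The Statistics section bases the sample size on a single ROC curve and lists the measures to be reported: "sensitivity, specificity, area under receiver operator curve, predictive value, likelihood ratio, odds ratio". The first null hypothesis is "There is no correlation between DNA fragmentation and clinical pregnancy/live birth after IUI". No covariate, stratification or multivariable model is named anywhere, and the odds ratio is not described as crude or adjusted.

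The list of items to be registered includes the "Hunault score and modified Hunault-score" and "Infertility: duration, primary versus secondary, female/male/mixed/unexplained". Neither is given a role in an analysis. Female age appears only as an eligibility limit ("Women: age between 18 and 40 years") and is not named in that list.

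**The concern.** The objective is a question of added value: does the test improve selection beyond what the clinic already measures? A single-marker AUC, sensitivity or odds ratio answers a different question, namely how well fragmentation alone separates couples who conceive from those who do not.

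The source population is mixed (unexplained infertility, mild male infertility, mild endometriosis; women aged 18 to 40), so prognosis will differ between couples. If fragmentation tracks that prognosis, some of its crude association is information that the clinic already has. A positive crude result could then be used to steer couples towards or away from IUI although the test adds little. The score and duration that could separate the two explanations are being collected. If no model is fixed beforehand, covariates can be chosen after the outcomes are known.

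**Working it through.** **The plan's own figure.** The Statistics section gives 38 to 130 patients for one AUC of 0.70-0.75, with case:control ratios of 1:1 to 1:3, alpha 0.05 and power 0.80. Assuming a null AUC of 0.5 and a two-sided test (neither is stated), the Obuchowski formula at AUC 0.75 and 1:1 uses

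- null variance 0.0792 × 2 = 0.1584; alternative variance 0.1348
- n per group = (1.96 × √0.1584 + 0.842 × √0.1348)² / 0.25² = 19.0, so 38 in total.

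The minimum reproduces. The maximum does not: the largest value from the variants tried was 88. That is a separate matter. What counts here is that the calculation concerns one marker with no covariates.

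**Inputs for the size of the problem**

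| Input | Value | Source |
|---|---|---|
| Couples | 120 | Statistics |
| Pregnancy rate | 9% (middle of 5-13% per cycle); 30% and 50% | Introduction for 5-13% and for about 50% after 4-6 cycles; 30% assumed |
| Independent effect of fragmentation | none | assumed |
| Correlation r of fragmentation with prognosis | 0.2-0.4 | assumed |
| Prognosis odds ratio per SD | 1.5-2.0 | assumed |

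**Hand approximation.** With normal markers, couples who do and do not conceive differ by about ln(OR) SD in prognosis, and so by about r × ln(OR) SD in fragmentation. The crude AUC is then about Φ(r × ln(OR) / √2).

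- Low end: Φ(0.2 × 0.405 / 1.414) = Φ(0.057) = 0.52
- High end: Φ(0.4 × 0.693 / 1.414) = Φ(0.196) = 0.58
- An AUC of 0.70 needs r × ln(OR) = 0.524 × 1.414 = 0.74. At an odds ratio of 2.0 that means r = 0.74 / 0.693 = 1.07, which is impossible.

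**Simulation** (1,500 trials per scenario; crude Mann-Whitney test against the Wald test from a logistic model with one prognostic covariate)

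| Pregnancy rate | Crude test significant | Adjusted test significant | Mean crude AUC |
|---|---|---|---|
| 9% | about 5-12% | about 4-6% | 0.52-0.57 |
| 30-50% | about 7-26% | about 4-6% | 0.52-0.57 |

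The Monte Carlo standard error near 12% is √(0.12 × 0.88 / 1,500) = 0.8 percentage points, so repeat runs differ by about a point. With correlation 0, both tests stay near 5%. Adding the covariate widened the fragmentation standard error by 3-13%. The linear-model factor 1/√(1 − r²) gives 2% at r = 0.2 and 9% at r = 0.4.

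**Events available for a model**

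- Case:control ratio 1:3 to 1:1: 120 × 0.25 = 30 to 120 × 0.50 = 60 pregnancies. With three terms, that is 10 to 20 events per term.
- One cycle per couple at 5-13%: 120 × 0.05 = 6 to 120 × 0.13 = 15.6, so about 6 to 16 events. With two terms, that is 3 to 8 per term.

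These counts are for clinical pregnancy. The documents give no live birth rate.

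**The case against.** The strongest reply is that this is a prediction study. Its null hypothesis is one of no correlation, and a marker that correlates with prognosis really does correlate with pregnancy. This stands. A reader might infer that the 5-26% is an inflated type I error for the planned test. It is not: under those assumptions the plan's null is false, and rejecting it is correct. The figures are false-positive rates only for an independent effect, which the plan does not state as a hypothesis.

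A reader might also infer that prognosis alone could yield the accuracy the study is designed to find. The figures do not support that. Mean crude AUC stays at 0.57 or below, and the observed AUC reached 0.70 in at most about 1% of trials at 30-50% pregnancy. At 9% it did so in 3-10%, but about 11 events make chance a large part of that.

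Two further limits hold. The plan never says that its analysis is unadjusted; it is silent, and the crude reading follows from the measures listed. Nor do the documents show that female age is a registered item. It must be known to apply the age limit, and may fall under the Belrap items, whose content is not given.

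What the reply does not meet is the objective itself. A comparison with semen criteria needs an analysis containing both fragmentation and a semen measure, and none is described.

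**Conclusion.** The point holds as a gap between the objective and the analysis. The planned measures can describe how well fragmentation predicts pregnancy. They cannot show that it improves on semen criteria, or that it carries information beyond the couple's general prognosis.

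That conclusion comes from the text and needs no assumption. Its numerical size does: the 5-12% and 7-26%, against 4-6% after adjustment, rest on an assumed correlation of 0.2-0.4 and an assumed odds ratio of 1.5-2.0 per SD. The documents give neither, so the actual amount of confounding is unknown and could be nil. The crude ROC analysis is not invalid and need not be replaced. The change is worth making before outcomes are analysed, because it is cheap and lets the result bear on the stated objective.

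**What to change.** Keep the crude ROC analysis as planned and add to the Statistics section:

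- **Model.** A logistic model with one named fragmentation measurement, one named version of the Hunault score, and one standard semen measure. Pre-wash total motile sperm count is an example, since the plan already uses it to define a normal semen analysis. The documents do not give the components of the score. Check whether the chosen version contains a semen item, because adjustment would then remove some sperm-related signal.
- **Reporting.** The adjusted odds ratio for fragmentation with its confidence interval, and the change in AUC when fragmentation is added to the model without it.
- **Main outcome for the model.** The cumulative outcome, where events are likely to support three terms.
- **Per-cycle outcomes.** A Firth-penalised model with fragmentation and the score only, and the AUC gain labelled as imprecise.
- **Female age.** If it is to be used separately from the score, add it to the registered items.

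The cost is analysis wording, one or two degrees of freedom, and a fragmentation standard error about 3-13% wider per prognostic covariate. The existing sample size calculation does not cover the adjusted analysis, and the plan should say so.
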